13.3 Data management

Clinical Trial Unit (CTU) – Bern University, will be in charge for data management and analysis.

Every investigator has access to data of patients enrolled in the own site. CTU in Bern has access to all patient data and can lock patient's data at the end of the trial. Once locked, data can no longer be modified by site investigator.

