2.6 Timing of final analysis

The primary endpoint analyses will be performed after all 45 days follow-up visits are conducted and completely entered into the data capture system; and after all data are cleaned and events have been adjudicated. Longer follow-up analyses at e.g. 13 months, 2 years, 3 years, 4 years and 5 years will be conducted as requested, after all data have completely entered into the data capture system; and after all data are cleaned and events have been adjudicated.

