2.8 Blinding

Allocation to the two randomized devices Amulet vs Watchman/FLX is concealed. After the randomization result is available, the study personnel, monitors, the trial statistician receiving the raw data download are not blinded to the randomized device.

However, independent blinded analyses will be conducted by a second statistician who does not know the allocation result of the randomization (e.g. coded X vs Y). Moreover, also the clinical event adjudication committee adjudicating the events is blinded to the randomized device.

The Sponsor will be provided with blinded tables of the primary outcome analyses (e.g. coded X vs Y with no denominators), which the Sponsor can use for final plausibility checks and queries for e.g. outliers to be send to the centres. If this final cleaning process is performed, the Sponsor will receive the unblinded results.

CTU Bern	Swiss APERO SAP	Version: 2.0	
	Template: CS_STA_TEM-11	Valid from: 17.08.2021	

3. Data management

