3.2 Data validation

Before locking, the data will be checked for completeness using e.g. missing tables functions. The plausibility of the primary and secondary outcomes will be checked using outlier analyses and histograms, and will be queried if they are outside the expected range, including dates of events. Only events occurring after the implantation (attempt) of the LAAC device will be analysed, in case no LAAC procedure was started the randomization date will be used instead.

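### SAP 2.8 shows the sponsor primary results by coded arm before cleaning is closed and lets it query centres afterwards, which does not fit SAP 2.6

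*Combined protocol and SAP*

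**What the plan says.** SAP 2.8 (Blinding) sets out a sequence.

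- After randomisation, "the study personnel, monitors, the trial statistician receiving the raw data download are not blinded to the randomized device". A second statistician analyses the data without knowing the allocation, and the clinical event committee is blinded to the randomised device.
- "The Sponsor will be provided with blinded tables of the primary outcome analyses". The masking is given as an example: "coded X vs Y with no denominators".
- These are tables "which the Sponsor can use for final plausibility checks and queries for e.g. outliers to be send to the centres".
- Unblinding is then tied to that querying step: "If this final cleaning process is performed, the Sponsor will receive the unblinded results".

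Three other places bear on the timing.

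- SAP 2.6 runs the primary endpoint analyses once the 45-day visits are complete and entered, "and after all data are cleaned and events have been adjudicated".
- SAP 3.2: "Before locking, the data will be checked for completeness using e.g. missing tables functions". It adds outlier analyses, histograms and range queries, and describes none of them as split by arm.
- Protocol 13.3: "Once locked, data can no longer be modified by site investigator".

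**The concern.** Queries should be triggered by the data values, not by how a query might move the treatment comparison. Under SAP 2.8 the sponsor can see the size of the difference between two coded arms and then decide what to query. It does not have to know which code is which device: seeing that X and Y differ, or narrowly fail to, is enough to affect how hard a doubtful record is pursued.

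What is at stake is mainly whether the trial can show that its primary dataset was fixed before anyone steering the cleaning saw a result. That matters more than usual here. The trial is open-label, it tests superiority of Amulet, and protocol section 15 names that device's manufacturer as the source of the grant.

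**Working it through.** **1. Order of events.** SAP 2.6 gives: clean and adjudicate, then analyse. SAP 2.8 gives: analyse by coded arm, query centres, finish cleaning, unblind. Both cannot describe the same primary analysis. Queries to centres serve a purpose only while centres can still change data, and protocol 13.3 ends that at lock. So SAP 2.8 implies that the tables come before lock. SAP 3.2 places its own checks before lock but does not mention the coded tables.

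**2. What missing denominators hide.** Inputs: 1:1 allocation (SAP 2.2); 200 patients, 50% vs 30% (SAP 2.3). Suppose only event counts are shown and the Watchman/FLX arm has n patients, with 200 − n in the Amulet arm. The count ratio is 0.30(200 − n) / 0.50n, against a true risk ratio of 0.60. The range of 95 to 105 for n is my assumption.

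- n = 95: 31.5/47.5 = 0.66
- n = 100: 30/50 = 0.60
- n = 105: 28.5/52.5 = 0.54

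The size of the difference can be read closely from counts alone. What the codes hide is its direction.

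**3. Which endpoint data a centre query can reach.**

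- *Patency value:* derived by a fixed rule from Hounsfield values in the core laboratory consensus record (SAP 3.3). A centre query does not change it directly.
- *Crossover:* entered by the centre in the procedure eCRF, then adjudicated (SAP 3.3). The committee is blinded, but it works from what the centre supplies.
- *Evaluable or not:* protocol 12.5 drops patients with a missing primary endpoint from the primary analysis, and the Table 5 footnote in SAP 5.8 foresees scans in which patency cannot be assessed. A query that recovers a scan or settles a withdrawal changes the analysis set without touching any reading.

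**4. The plan's own figure.** With 100 per arm, two-sided 5% (sidedness is not stated, so two-sided is assumed) and p̄ = 0.40: z = (0.20·√100 − 1.96·√(2·0.40·0.60)) / √(0.50·0.50 + 0.30·0.70) = (2 − 1.358)/0.678 = 0.947, so power is 82.8%. The stated figure of more than 80% reproduces.

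**5. Sensitivity to single records.** Two-sided p-values, 100 per arm unless shown:

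| Watchman/FLX vs Amulet | Fisher | χ², uncorrected |
|---|---|---|
| 43 vs 30 | 0.078 | 0.056 |
| 44 vs 30 | 0.057 | 0.040 |
| 45 vs 30 | 0.041 | 0.028 |
| 44/99 vs 30/100 | 0.041 | 0.035 |
| 50 vs 30 (planned) | 0.006 | 0.004 |

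Under Fisher, the test named under Table 4 in SAP 5.7, one added event at 44 vs 30 crosses 0.05, and so does one non-event becoming missing. Under χ², the crossing lies one event lower. From the planned 50 vs 30, six Watchman/FLX events must be lost (50 to 44) before Fisher's p exceeds 0.05.

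**6. Worst case, on an assumed number of changes.** I enumerated all outcomes for 100 per arm with equal true rates of 30%, 40% and 50%, allowing up to k outcomes to be changed so as to widen the difference seen. Fisher's type I error is 3.5–4.0% with no change, 5.1–5.6% with k = 1 and 9.8–10.6% with k = 3. If only differences favouring one device are widened, k = 3 gives 6.7–7.2%. The documents give no k, and the safeguards in step 3 make such changes harder than this calculation assumes.

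**The case against.** The strongest reply is that the plan already masks the arms and that centres control little of the endpoint. Much of this stands. On paper the sponsor cannot tell which device a difference favours. Patency is read centrally by three assessors, and crossover counts only after blinded adjudication. The eCRF has an audit trail (protocol 13.1), and the outcomes are double-programmed (SAP 6.7). SAP 2.8 may also intend no more than a last look after the main cleaning, and its final sentence can be read as making that step conditional.

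Three stronger readings are tempting and are not supported.

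- *That the arms are effectively unmasked, because Table 4 has its own crossover row.* Table 4 is the reporting shell. Nothing says that the coded tables contain that row, and crossover counts identify an arm only to someone who already knows them by arm. SAP 2.8 does not name the sponsor among the unblinded parties.
- *That one corrected record would change the trial's conclusion.* This is true only at a borderline, and where the borderline lies depends on the test. It is not the planned scenario.
- *That data will be altered to suit.* Nothing in the documents suggests misuse.

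What the reply does not answer is the order of steps. The coding is offered only as an example, missing denominators conceal little under 1:1 allocation, and no passage closes queries or locks the database before the tables are made.

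**Conclusion.** The point holds as one of sequence and consistency. SAP 2.8 releases coded between-arm primary results before cleaning is closed and allows centre queries after that; SAP 2.6 says the reverse; the lock is not placed relative to the tables. The route left open is narrow: centre-entered crossover records and evaluable-endpoint status.

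Its effect on the result cannot be quantified in advance. It would be nil at the planned effect if only one record changed, and decisive only if the result fell near the boundary. This rests on three assumptions: two-sided 5% testing, about 100 per arm, and coded tables in the form that SAP 2.8 gives as its example. It is worth correcting because it is avoidable at almost no cost, not because the safeguards are absent.

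**What to change.** In SAP 2.8, limit what the sponsor receives for cleaning to distributions pooled over both arms and patient-level outlier listings without allocation. Then close all queries, lock the database and record the date. Produce tables split by arm, coded or not, only after that. Align SAP 2.6, 2.8 and 3.2 so that all three give this order.

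If coded tables have already gone out, report the dates of the tables, the queries and the lock, and list every primary-endpoint record changed in between, including any change in whether a patient was evaluable.

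The cost is SAP wording and a different order of the same work. Sample size, alpha and patient procedures do not change. The sponsor loses a by-arm plausibility look before lock; the checks in SAP 3.2 cover the same ground without the split.

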3.1 Data export

Data are stored in the web-based electronic data capturing portal of ICE-Advice Pharma. Data are exported from the ICE-Advice Pharma data capture portal in comma delimited text files with a codebook also in comma delimited text files, by the statisticians.

3.2 Data validation

Before locking, the data will be checked for completeness using e.g. missing tables functions. The plausibility of the primary and secondary outcomes will be checked using outlier analyses and histograms, and will be queried if they are outside the expected range, including dates of events. Only events occurring after the implantation (attempt) of the LAAC device will be analysed, in case no LAAC procedure was started the randomization date will be used instead.

3.3 Data preparation

LAA patency is derived from the average Linear attenuation coefficient within the LAA distal to the device's lobe (artphase_mean2) ≥ 100 HU OR average Linear attenuation coefficient within the LAA distal to the device's lobe $\geq 25\%$ of the average Linear attenuation coefficient within the LAA (artphase_mean2/artphase_mean1 ≥ 0.25), as recorded inside the follow-up 45 days visit of the Consensus estimate (this is the consensus of the three Core laboratory assessments by three different assessors). LAA patency is a marker of leaks in/out of the LA and therefore a marker of potential thrombus material migration from the LAA to blood circulation system.

Cross-overs are captured in the procedure eCRF and Adjudicated by the clinical event adjudication committee, both successful and failed attempts to cross-over.

CTU Bern	Swiss APERO SAP	Version: 2.0	
	Template: CS_STA_TEM-11	Valid from: 17.08.2021	

The primary endpoint is defined as LA patent or adjudicated cross-overs including failed cross-overs.

Table 1: Derivation of LA patency used in the primary outcome.

Outcome	eCRF sheet	Variable	Variable type	Remarks
LAA patency				
patent = 1	CCTA	fu_reader = 6 = Consensus AND (artphase_mean2 ≥ 100 OR artphase_mean2/artphase_mean1 ≥ 0.25)	Categorical Continuous	Consensus assessment of three assessors LAA HU mean distal from device's lobe in arterial phase = artphase_mean2 LA HU mean in arterial phase = artphase_mean1
not patent = 0				artphase_mean2 not missing and not patent as reverse of the above

Clinical events are also adjudicated and these adjudicated events up to 45 days after the LAAC procedure (or randomization date if no procedure was initiated) will be analysed, excluding events occurring before the LAAC procedure (or randomization date if no procedure was initiated) and excluding events occurring on day 46 and later. Adjudicated events beyond 45 days are used for the longer-term follow-up analyses and censored accordingly (e.g. at 1 year, at 5 years).

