Recently our group has retrospectively analyzed 56 patients who underwent LAAC of whom 40 who received TEE as well as a clinically indicated CCTA after intervention.¹⁷ ACP Amplatzer was used in 38 (67.9%) patients, while Amulet in 12 (21.4%) and Watchman in 6 (10.7%) patients. TEE guidance was used in 3 cases only, all receiving the Watchman device. Device success was achieved in 100% of cases, while technical and procedural success

was obtained in 53 cases (94.6%). The median time from LAAC to CT was 217 [86-401] days, whereas median time from LAAC to TTE was 90 [74-131] days. Based on 100 HU cut-off value, 24/56 (43%) patients had patent LAA after intervention (i.e. >100 HU measured in the LAA). The mean HU of LAA was significantly higher in patent LAA as compared with occluded LAA (209.0 ± 67.3 vs. 63.8 ± 21.8 ; $p < 0.001$), whereas HU, as measured in LA, did not differ between the two groups. LAA/LA HU ratio was also significantly higher in patients with patent LAA (0.65 ± 0.2 vs. 0.25 ± 0.1 ; $p < 0.001$). Using CT patency as gold standard, we calculated that a cutoff of 0.43 for the LAA/LA HU ratio provided a 92% of sensitivity and 94% specificity, with an AUC of 0.94. When the echocardiographic criteria recommended by the ACP/Amulet device manufacturer were applied to CT images, at least 2 mm separation between the lobe and the pacifier disk was identified in 46/50 (92%) of cases; the disc was concave at visual estimation in 47/50 (94%) of cases; the lobe was implanted at least 2/3 deeper than the circumflex artery crossing axis in 30/50 (60%) cases; the lobe and the disk were aligned in 36/50 (72.0%) of cases; finally > 10 % lobe compression was present in 24/50 (48%) of patients. None of the above reported criteria, either separately or in combination, differ between patients with or without patent LAA at CT images. Multiplanar reconstruction of CT images identified lack of proximity between the disk and LAA ostium as obvious reasons for LAA patency in 22/24 cases (91.7%), of whom 15 (68%) were in the posterior quadrants. Therefore, these three retrospective series of patients who underwent LAAC do consistently suggest that only CCTA can reliably identify all patients with LAAC who present shortly after or at later time point peridevice leaks.

There are currently no randomized controlled trials assessing the degree of LAA closure between Amulet and Watchman/FLX.

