9.2 Assessments of outcomes

Assessment of primary outcome

The primary outcome is the composite of LAA patency at 45 day evaluated with CCTA or the crossover from one device to the other device based on morphological/anatomical considerations during device implantation.

Patency LAA will be estimated at CCTA by measurement of the linear attenuation coefficient (Hounsfield unit, HU) in the LAA distal to the device and comparison of contrast density to atrial chamber. LAA patency was defined with $HU \geq 100$ or $HU \geq 25\%$ of the atrium, as reported in a previous publication.¹⁵ The occurrence of LAA patency will be centrally evaluated and adjudicated by an Imaging Core Lab (ICL) composed of three imaging experts who will independently score each of the studies as positive or negative for LAA patency. In the event of inconsistent primary end point adjudication between the three readers, a consensus between all of them will be required. Adjunctive CCTA criteria of complete occlusion (as described in section 10.2) will be collected in order to validate them. A TEE evaluation of PDL presence will be performed at 45-days in order to compare the two imaging technique. The crossover is defined as the switch from the randomized device to the other device based on morphological/anatomical considerations during device implantation. It will be centrally adjudicated by CEC as justified if there will be evidence that the randomly allocated device has been positioned at least once in the LAA but LAA ostium sealing remained suboptimal (peri-device leak ≥ 3 mm) or concerns were present over the device stability and consequent risk of device embolization.

Assessment of secondary outcomes

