2.3 Sample size

Considering an incidence of the primary composite end-point in the range of 50% in the Watchman/FLX group, which is a conservative estimate based on previous reports, we estimate that 200 patients will provide greater than 80% power to prove superiority of Amulet as compared to Watchman/FLX assuming a 40% risk reduction (i.e. corresponding to an event rate in the range of 30%) and a significance level of 5% (alpha).

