5.8 LAA assessments at 45 days of Follow-up

A Table of the LAA assessments (CCTA by the Core laboratory, TEE by the local teams) at 45-day visit will be produced, randomized to Amulet vs randomized to Watchman.

Table 5. Imaging assessment at 45 days visit

	Watchman/FLX N = xx	Amulet N = xx	Amulet vs Watchman Mean difference (95% p-value
CCTA assessment			
45day CCTA performed	n = xx, xx (%)	n = xx, xx (%)	x.x% (x.x%; x.x%)
Linear attenuation HU— mean (SD) ¶	n = xx, mean + sd	n = xx, mean + sd	x.XXX
Patent LAA — no. (%) ¶	n = xx, xx (%)	n = xx, xx (%)	x.XXX
LAA HU \geq 100 arterial phase — no. (%) ¶	n = xx, xx (%)	n = xx, xx (%)	x.XXX
LAA HU \geq 25% arterial phase — no. (%) ¶	n = xx, xx (%)	n = xx, xx (%)	x.XXX
Peridevice leak (PDL) — no. (%) ¶	n = xx, xx (%)	n = xx, xx (%)	x.XXX
Mixed leak (ML) — no. (%) ¶	n = xx, xx (%)	n = xx, xx (%)	x.XXX
Intradevice leak (IDL) — no. (%) ¶	n = xx, xx (%)	n = xx, xx (%)	x.XXX
Patent LAA with no visible leak — no. (%) ¶	n = xx, xx (%)	n = xx, xx (%)	x.XXX
Linear attenuation HU — mean venous phase (SD) ¥	n = xx, mean + sd	n = xx, mean + sd	n = xx, mean + sd
LAA patency venous phase — no. (%) ¥	n = xx, xx (%)	n = xx, xx (%)	x.XXX
LAA HU \geq 100 venous phase — no. (%) ¥	n = xx, xx (%)	n = xx, xx (%)	x.XXX
LAA HU on venous phase \geq 150% of LAA HU on arterial phase images — no. (%) ¥	n = xx, xx (%)	n = xx, xx (%)	x.XXX
Potential thrombus — no. (%)	n = xx, xx (%)	n = xx, xx (%)	x.XXX
Device related thrombus — no. (%)	n = xx, xx (%)	n = xx, xx (%)	x.XXX
TEE assessment			
45day TEE performed	n = xx, xx (%)	n = xx, xx (%)	x.XXX
Peridevice leak PDL — no. (%)	n = xx, xx (%)	n = xx, xx (%)	x.XXX
first PDL — no. (%)	n = xx, xx (%)	n = xx, xx (%)	x.XXX
PDL leak width — mm mean(SD)	n = xx, mean + sd	n = xx, mean + sd	n = xx, mean + sd
second PDL — no. (%)	n = xx, xx (%)	n = xx, xx (%)	x.XXX
PDL leak width — mm mean(SD)	n = xx, mean + sd	n = xx, mean + sd	n = xx, mean + sd
Any PDL width \geq 3mm — no. (%)	n = xx, xx (%)	n = xx, xx (%)	x.XXX
Device related thrombus — no. (%)	n = xx, xx (%)	n = xx, xx (%)	x.XXX

Data expressed as n (%), p-value from Fisher's tests) or means \pm standard deviations (p-value from unpaired t-tests) or median[IQR] (p-value from Mann-Whitney U-test).

CCTA: cardiac computer tomography angiography assessed by Core Laboratory. TEE: Transoesophagus Echocardiography assessed by local team.

Mixed PDL: PDL transferring into intradevice leak, or intradevice leak transferring into

[figure not shown]

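### Does the 0.25 ratio leg of the patency rule undermine the primary result or the planned power?

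*Combined protocol and SAP*

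**What the plan says.** The rule in SAP 3.3, Table 1, is "artphase_mean2 ≥ 100 OR artphase_mean2/artphase_mean1 ≥ 0.25". There artphase_mean2 is mean appendage density distal to the lobe in the arterial phase and artphase_mean1 is mean left atrial density. Protocol 9.2 and SAP 2.7 state the same two-legged rule and credit it to a cited publication.

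The background (protocol 3.1) reports the sponsor's own series, read on the density leg only: "Based on 100 HU cut-off value, 24/56 (43%) patients had patent LAA after intervention". In that series, "LAA/LA HU ratio was also significantly higher in patients with patent LAA (0.65 ± 0.2 vs. 0.25 ± 0.1", and "Using CT patency as gold standard, we calculated that a cutoff of 0.43 for the LAA/LA HU ratio provided a 92% of sensitivity".

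The sample size (protocol 12.2, SAP 2.3) takes the incidence of the primary composite to be "in the range of 50% in the Watchman/FLX group, which is a conservative estimate based on previous reports", and about 30% with Amulet.

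SAP 6.2.3 lists two sensitivity analyses: multiple imputation on request, and adjustment for a late 45-day CCTA. Neither varies the patency rule. SAP 5.8 provides Table 5: "A Table of the LAA assessments (CCTA by the Core laboratory, TEE by the local teams) at 45-day visit will be produced". Its rows include patent LAA, the 100 HU leg and the 25% leg, each by arm.

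**The concern.** An OR rule is only as strict as its looser leg. The ratio leg is the looser one whenever 0.25 times atrial density is below 100 HU, that is, whenever atrial density is below 400 HU. The series implies densities well under that, so in practice the ratio would decide patency. It would do so at a cut that the sponsor's own data place in the middle of the appendages called occluded, and well below the ratio cut-off of 0.43 derived there.

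Two things could be at stake. If the 50% and 30% had been read on 100 HU alone, and the ratio leg added the same share of events to the remaining patients in both arms, the contrast would shrink and power would fall well below 80%. Separately, no planned analysis shows the full composite on 100 HU alone, so the result might seem to hang on the ratio leg without a reader being able to see it.

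**Working it through.** **1. The plan's power.** Inputs from SAP 2.3: 50% against 30%, 200 patients at 1:1 (100 per arm), 5% level, taken as two-sided. With pooled variance under the null:

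z = [0.20 − 1.96·√(2·0.4·0.6/100)] / √[(0.5·0.5 + 0.3·0.7)/100] = (0.20 − 0.1358)/0.0678 = 0.947, so power is 82.8%.

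Exact enumeration gives 83.2% for chi-square and 79.2% for Fisher's test. The claim of more than 80% reproduces with the standard formula, which needs 93 per arm.

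**2. Atrial density implied by the series.** Occluded group: 63.8/0.25 = 255 HU. Patent group: 209/0.65 = 322 HU. Both are below 400, so the ratio leg is the looser one.

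**3. Share d of appendages below 100 HU with ratio of at least 0.25, if the series carries over.** The shape of the distribution is assumed.
- Normal ratio, mean 0.25, SD 0.1: d = 50%.
- Lognormal with the same moments: σ = √ln(1 + 0.1²/0.25²) = 0.385, so d = 1 − Φ(σ/2) = 42%.
- From densities: a normal truncated at 100 HU whose truncated mean and SD equal the reported 63.8 and 21.8 has parent mean 70.7 and SD 26.9. With atrial density 321 HU the ratio cut is 80 HU and d = 26%. With 255 HU the cut is 64 HU and d = 54%.

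The 26% is a low figure: 63.8/321 = 0.20, which does not match the reported mean ratio of 0.25. A fair summary is a quarter to a half. Patency in the series would move from 24/56 = 43% to (24 + 32d)/56, which is 58% at d = 0.26 and 71% at d = 0.50.

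**4. What that would do to power.** Only if 50% and 30% were 100 HU rates, with equal d in both arms, each rate p becomes p + (1 − p)d:

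| d | Watchman/FLX | Amulet | Power |
|---|---|---|---|
| 0 | 50% | 30% | 82.8% |
| 0.26 | 63.0% | 48.2% | 56% |
| 0.42 | 71.0% | 59.4% | 40.5% |
| 0.50 | 75.0% | 65.0% | 33.7% |

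Both documents attach the rates to the primary composite, and its only arterial-phase patency definition is the OR rule. On that reading the first row applies and nothing is lost.

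**5. What the planned tables already show.** Let P be the count with patent LAA, H the count with at least 100 HU, X the adjudicated crossovers and C the composite count, all in one arm. P is the union of the two legs, so the count patent by ratio only is R = P − H, from Table 5. Table 4 gives C, P and X. Because SAP 4.2 counts every crossover as an event, the overlap of patency and crossover is P + X − C. The composite on 100 HU alone is C − R + k, where k is the number of ratio-only patients who also crossed over. k lies between 0 and the smaller of R and P + X − C, so the tables bound the missing count.

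**6. The denominator.** The SAP 3.3 prose names the appendage as the denominator of the ratio. Table 1 in the same section defines artphase_mean1 as atrial density, and SAP 2.7 says the same. The variable names fix what is programmed.

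**The case for a change.** The strongest case for a change is that a primary endpoint resting on a cut where two CT criteria often disagree deserves a prespecified check. Both densities are already stored, so the check costs almost nothing, and the tables give bounds rather than a risk difference with a confidence interval. The planning rates are also hard to trace: the background CT rates are 52%, 62% and 43%, the reports behind the 50% are not named, and the reference credited with the OR rule is described in protocol 3.1 as supporting a 100 HU threshold. Finally, if 30% for Amulet is an OR-rule rate, the implied 100 HU rate at d = 0.26 is (0.30 − 0.26)/(1 − 0.26) = 5%, and no value is possible once d exceeds 0.30. The series, mostly Amplatzer devices, showed 43% on 100 HU alone.

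Part of this stands. The patency rule behind the earlier reports is not stated, and the extra analysis would be harmless. The last argument shows that the series and the 30% cannot both carry over; it does not show which one fails. The series had 38 first-generation ACP devices, 12 Amulet and 6 Watchman, with TEE guidance in 3 cases, and "The median time from LAAC to CT was 217 [86-401] days" rather than 45. The documents give no patency rate or ratio for Amulet alone. The disagreement is also not proven misclassification: occluded there simply means not above 100 HU, and 0.43 was tuned to that call, so re-analysing at 0.43 would largely repeat the 100 HU analysis.

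**Conclusion.** No change to the plan is needed. The ratio leg does coincide with the mean ratio of appendages below the 100 HU cut in the sponsor's series, and the two criteria could disagree in about a quarter to a half of such appendages. That rests on transfer from a small retrospective series of mostly first-generation devices and on an assumed distribution.

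The OR rule is a fair prespecified choice, attributed to a source and stated alike in protocol 9.2, SAP 2.7 and SAP 3.3, Table 1. The stated power reproduces at 82.8%, and the fall to between 56% and 34% appears only if the planning rates are read against their own label. Any reliance on the ratio leg will be visible by arm in Table 5. Only its overlap with crossover is untabulated, and Tables 4 and 5 bound that. A 100 HU row for the composite is something analysts can add if the Table 5 legs differ noticeably between arms. The denominator in the SAP 3.3 prose is a clerical slip that Table 1 resolves.
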